6.3.4. Blinding

Subjects, investigators and site personnel, and the Sponsor (with exceptions described below) will be blinded to individual subject treatment assignments in the PCP. All subjects will dose IP BID to maintain the blind.

The study will be unblinded to the Sponsor at the time of the PCP Week 12 Analysis (see Section 9.4). Therefore, the PCP will be double-blind through PCP Week 12 and will remain blinded to subjects, investigators, and site staff throughout the PCP.

Sponsor (or designee) personnel will have access to unblinded individual subject treatment assignments for the purposes of study-required activities, including management of IP inventory, production of summaries of data for DRC review, and performance of bioanalytical analysis of PK and gene/protein concentrations. These personnel will not be directly involved in the conduct of the study.

A DRC will periodically convene to review unblinded overall safety and emerging efficacy results (refer to Section 9.5.1).

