9. STATISTICAL CONSIDERATIONS

9.1. Statistical Hypotheses

9.1.1. Placebo-Controlled Period

The PCP is designed to demonstrate the superiority of each GB004 treatment group to placebo on the primary endpoint of the proportion of subjects with clinical remission at PCP Week 12. The PCP is also designed to demonstrate the superiority of each GB004 treatment group to placebo on the primary endpoint of the proportion of subjects with clinical remission at PCP Week 36.

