2.5.2. Blinding

The PCP is considered double-blind through PCP Week 12, as the study will be unblinded to the Sponsor at the time of the PCP Week 12 Analysis. The Sponsor (with exceptions described below) will be blinded to individual subject treatment assignments until the PCP Week 12 Analysis. Subjects, investigators and site personnel, personnel performing central endoscopic and histologic evaluations, and personnel performing central laboratory and ECG evaluations will remain blinded to individual subject treatment assignments throughout the PCP.

Sponsor (or designee) personnel will have access to unblinded individual subject treatment assignments prior to unblinding of the Sponsor at the time of the PCP Week 12 Analysis for the purposes of study-required activities, including management of IP inventory, production of summaries of data for DRC review, performance of bioanalytical analysis of PK and gene/protein concentrations, and performance of population pharmacokinetic modeling, for which subject level treatment assignment data will be provided to clinical pharmacology personnel performing the modeling using only pseudonymized (also known as dummy) subject identifiers. These personnel will not be directly involved in the conduct of the study. The DRC, comprised of Sponsor representatives not directly involved in the conduct of the study and external expert physicians, will have access to unblinded study results and data during the course of the study.

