 - This ICE is considered to have occurred on the first date of qualifying dose increase.
- Post-baseline prolonged course of systemic corticosteroids, where ‘prolonged’ is defined as consecutive use for > 7 days, for an indication other than UC.

This ICE is considered to have occurred on the first start date of qualifying systemic corticosteroid use.

- A colectomy (partial or total) or an ostomy.

This ICE is considered to have occurred on the procedure date for the colectomy or ostomy.

- Discontinuation of PCP study treatment > 28 days prior to the timepoint of the endpoint.

The approach for handling intercurrent events described above will be applied prior to employing the approaches for handling of missing data described in [Section 8.1.1](#) above.

Identification of ICEs may be performed by programmatic derivation and/or manual review. For the PCP Week 12 Analysis, this will be performed prior to Sponsor unblinding.

The number and percentage of subjects with an ICE will be summarized overall and by each of the types of ICEs listed above. For the PCP Final Analysis, this will be further summarized with respect to ICE occurrence prior to PCP Week 12. A by-subject data listing of ICEs will be provided.

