8.3. Analysis Methods

8.3.1. Primary Endpoint

8.3.1.1. Primary Analysis

The primary objective of the PCP will be evaluated by testing the superiority of each GB004 treatment group to the placebo treatment group with respect to the primary endpoint of the proportion of subjects with clinical remission at PCP Week 12 based on a Cochran-Mantel Haenszel (CMH) chi-squared test ([Mantel, 1959](#)) stratified by the randomization stratification factor of systemic corticosteroid use at baseline (yes/no) with a two-sided 0.050 level of significance for each comparison.

The Mantel-Fleiss criterion ([Mantel, 1980](#)) will be used to assess the validity of the chi-square approximation for the distribution of the CMH test statistic. In the case that the Mantel-Fleiss criterion is not at least 5, indicating lack of validity of the chi-square approximation due to stratum cell sizes that are too small, Pearson's chi-squared test will be used instead of the CMH chi-squared test in the primary analysis of the primary endpoint. In the rare case that expected cell frequencies are too small, Fisher's exact test will be used instead of Pearson's chi-squared test.

For the comparison of each GB004 treatment group versus placebo, the p-value from the CMH chi-squared test (or Pearson's chi-squared test and/or Fisher's exact test, as described above) will be reported. The number and proportion of subjects meeting the primary endpoint and corresponding 95% Wilson (Score) CIs ([Wilson, 1927](#)) will be summarized by treatment group.

The unstratified, absolute difference in proportion between each GB004 treatment group and placebo will be summarized, with the 95% CI for the unstratified, absolute difference based on the Newcombe continuity-corrected method ([Newcombe, 1998](#)). The estimated Mantel-Haenszel common odds ratio across strata and corresponding 95% CI will also be summarized.

The primary analysis of the primary endpoint will be based on application of ICE handling followed by NRI.

A bar graph of the proportion of subjects meeting the primary endpoint by treatment group will be presented.

Primary endpoint data will be presented in a by-subject data listing.

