8.3.2. Secondary Endpoints

8.3.2.1. Primary Analysis

The secondary efficacy objectives of the PCP will be evaluated by testing the superiority of each GB004 treatment group to the placebo treatment group with respect to the secondary efficacy endpoints described and defined in [Section 2](#) with a two-sided 0.050 level of significance for each comparison. The primary analyses of these secondary efficacy endpoints will be performed using the same approach as the primary analysis of the primary endpoint.

Secondary efficacy endpoint data will be presented in a by-subject data listing.

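### The SAP requires intercurrent events to be identified before Sponsor unblinding only for the Week 12 Analysis, so manual calls for the Week 36 endpoints may be made with treatment codes known

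*SAP*

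**What the plan says.** SAP 8.1.4 lists the ICEs that turn a subject into a non-responder for a binary endpoint. On how they are found it says "Identification of ICEs may be performed by programmatic derivation and/or manual review", followed by "For the PCP Week 12 Analysis, this will be performed prior to Sponsor unblinding". No matching sentence covers the PCP Final Analysis.

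On unblinding, Protocol 6.3.4 says "The study will be unblinded to the Sponsor at the time of the PCP Week 12 Analysis"; Protocol 9.4 repeats this. SAP 2.5.2 agrees: "The Sponsor (with exceptions described below) will be blinded to individual subject treatment assignments until the PCP Week 12 Analysis". The same section names those who stay masked throughout the placebo-controlled period: "Subjects, investigators and site personnel, personnel performing central endoscopic and histologic evaluations, and personnel performing central laboratory and ECG evaluations will remain blinded". It does not mention whoever identifies ICEs.

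On use, SAP 8.3.1.1 says "The primary analysis of the primary endpoint will be based on application of ICE handling followed by NRI", and SAP 8.3.2.1 carries this over: "The primary analyses of these secondary efficacy endpoints will be performed using the same approach as the primary analysis of the primary endpoint". The secondary endpoints include five at Week 36: clinical remission, clinical response, histologic remission, endoscopic improvement and mucosal healing. Protocol 9.1.1 gives clinical remission at Week 36 its own hypothesis: "The PCP is also designed to demonstrate the superiority of each GB004 treatment group to placebo".

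**The concern.** The plan protects ICE calls from knowledge of treatment at Week 12 and is silent for Week 36, when the Sponsor already holds the codes. An ICE call changes the outcome directly: a subject who met the endpoint becomes a non-responder. If such a call involves judgement and the person making it can see the arm, differential classification is possible, even if unintended. The Week 36 comparisons are the only randomised evidence on longer-term effect, so it is worth closing a route that costs little to close.

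**Working it through.** **Step 1: is there a gap?** Set the sections side by side.

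| Item | Week 12 Analysis | PCP Final Analysis |
|---|---|---|
| Manual ICE review allowed (SAP 8.1.4) | yes | yes |
| Required before Sponsor unblinding (SAP 8.1.4) | yes | not specified |
| Sponsor blinded (SAP 2.5.2, Protocol 6.3.4) | until this analysis | no |
| Sites and central readers blinded (SAP 2.5.2) | yes | yes |
| Person making ICE calls named | no | no |

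The gap is in the text.

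**Step 2: how much judgement is left?** Much of SAP 8.1.4 can be programmed: colectomy or ostomy date, stopping study treatment more than 28 days before the timepoint, a 20% aminosalicylate increase for at least 7 days, and steroid courses with day limits. SAP 1 says the SAP was approved before Sponsor unblinding. Three places remain.

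- *Rescue medication.* The list is given as examples and is not closed. It is bounded because the rule concerns protocol-prohibited new UC therapy, which Protocol 6.5.2, 7.1.5 and Appendix 6 describe. What is left is mainly a drug of unclear purpose.
- *Newly started steroid course of 4 to 7 days.* For UC, more than 3 consecutive days is an ICE; for another indication, more than 7 days is. At 3 days or fewer neither applies, and above 7 days it is an ICE either way. Between 4 and 7 days the indication decides. Blinded sites record the reason for use (Protocol 6.8), so judgement enters only if that record is interpreted or overridden.
- *Steroid restart after a completed taper.* Tapering begins only after Week 12, so this belongs to the unprotected period. Protocol 6.5.2 and SAP 8.1.4 permit an increase up to the baseline dose when a taper is not tolerated. SAP 8.1.4 also counts new initiation of systemic steroids. Neither says which applies to a restart from zero, and the sponsor should reconcile the passages.

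The 28-day rule narrows the first two. Under Protocol 7.1.5 a subject who needs new UC therapy stops study treatment. Where that was followed, a start more than 28 days before Week 36 is already an ICE by date. Those cases therefore matter mainly for starts in the last 28 days, or where treatment continued.

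**Step 3: what can one call do?** The documents give no figure for this, so the arithmetic is illustrative.

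Inputs (Protocol 9.2.1, SAP 2.6): about 65 per arm, 10% placebo remission, 30.4% on each GB004 arm, two-sided 0.050, 8% dropout. The plan's figure reproduces: a pooled-variance two-proportion calculation without continuity correction gives 60 per arm, with 80.3% power. Allowing for dropout gives 60 × 1.08 = 64.8, or 65, and 60 / 0.92 = 65.2, or 66. SAP 2.6 applies the same assumptions to Week 36.

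One call at 65 per arm moves the difference by 1/65 = 1.54 percentage points. Expected placebo remitters are 0.10 × 65 = 6.5; take 6. The statistic is the single-stratum CMH form, Pearson chi-squared × (N−1)/N with N = 130.

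- 14 versus 6: pooled rate 20/130 = 0.1538; difference 8/65 = 0.1231; variance 0.1538 × 0.8462 × 2/65 = 0.004005; Pearson 0.01515/0.004005 = 3.782; × 129/130 = 3.753; p = 0.053.
- 15 versus 6: pooled rate 21/130 = 0.1615; difference 9/65 = 0.1385; variance 0.1615 × 0.8385 × 2/65 = 0.004168; Pearson 0.01917/0.004168 = 4.600; × 129/130 = 4.565; p = 0.033.

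One call decides a result at that boundary. SAP 8.2 limits the Week 36 analyses to subjects who consented to protocol version 2.0, so arms may be smaller. At assumed sizes of 60 and 55, one call is 1.7 and 1.8 points.

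**The case against.** The strongest reply is that the SAP is silent on this point and does not plan unblinded review. No sentence says that unblinded staff will make ICE calls, and the list in SAP 2.5.2 does not address ICE reviewers at all. The rules were fixed before unblinding, new UC therapy is bounded by the protocol, and blinded sites supply the reason for use. The restart question is one of rule interpretation before it is one of blinding. Subjects who moved to the open-label extension before Week 36 would generally be non-responders through missing data, whatever ICE call is made. Sensitivity Analyses #1 and #3 drop ICE handling, SAP 8.3.2.2 applies them to secondary endpoints, and a by-subject ICE listing is planned. These are secondary Phase 2 endpoints tested without multiplicity adjustment.

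All of this limits the weight of the point, but it does not close the gap. The sensitivity analyses and listing would show whether a result depends on ICE calls; they do not mask the calls behind the main Week 36 analysis. Nothing requires a manual call to follow the site's entry. An interpretation question is also safer settled without sight of codes.

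A reader might go further and infer that the Week 36 results will be biased, or that the p-values above measure the bias. The documents support neither. The one-call sensitivity is a property of any trial of this size near p = 0.05, and it presupposes a contestable subject who otherwise met the endpoint.

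**Conclusion.** The point holds as a minor gap: the SAP permits, but does not say, that manual ICE calls for the Week 36 endpoints will be made with codes known. The Week 12 primary analysis is protected and unaffected. The number of manual calls cannot be described as few or many, because the SAP gives neither a count nor a limit. The effect of one call, 1.5 percentage points at 65 per arm, assumes equal arms, a single stratum although the planned test is stratified by corticosteroid use, and the clinical remission endpoint only. Histologic remission and mucosal healing use a baseline-restricted subset (SAP 8.2), so one call there would move the difference at least as much. No probability of a contestable case can be derived from the documents, so no size of bias is claimed.

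**What to change.** Extend the condition in SAP 8.1.4, for example: *For the PCP Final Analysis, ICEs will be derived by program where possible. Any manual call, and the classification of cases that the rules leave open, will be made and locked on listings without treatment codes by existing Sponsor or designee staff who have not received subject-level assignments.*

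How each open case is classified, including a steroid restart after a completed taper, is for the sponsor to settle when reconciling the passages. The request is only that it be settled without sight of codes.

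The cost is a short SAP change with no new data or visits. The downside is that a few existing staff must be kept from subject-level codes until the calls are locked. The documents do not show who would still be without codes after the Week 12 Analysis, so these people should be named before the Sponsor is unblinded.

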8.2. Efficacy Endpoints

[Table 3](#) below provides a summary of the statistical models/methods of primary and sensitivity analyses to be used for primary, secondary, and exploratory efficacy endpoints.

Table 3: Efficacy Endpoints and Analysis Methods

Efficacy Endpoints	CMH	Logistic Regression	ANCOVA
Primary and Secondary	Primary Analyses, Sensitivity Analyses	Sensitivity Analyses	
Exploratory			
Proportion-based	Primary Analyses		
Change from baseline			Primary Analyses

Abbreviations: ANCOVA, analysis of covariance; CMH, Cochran-Mantel Haenszel

Analyses of efficacy endpoints for the PCP Week 12 Analysis (ie, efficacy endpoints evaluated at or up to and including PCP Week 12) will be based on the ITT population, unless otherwise stated below.

Analyses of efficacy endpoints for the PCP Final Analysis involving timepoints after PCP Week 12 will be based on the subset of subjects in the ITT population who consent to version 2.0 of the protocol, unless otherwise stated below.

Further analysis population details for specific efficacy endpoints are described below.

Certain secondary and exploratory efficacy endpoints will only be evaluated in a subset of subjects in the ITT population in order to ensure that achievement of the endpoint can be attributed to study treatment and that treatment effect estimation is not affected by any potential imbalance across treatment groups with respect to subjects fully or partially meeting requirements for the endpoint at baseline. This includes the following:

- Endpoints assessing histologic remission (including mucosal healing and disease clearance) will be evaluated in the subset of subjects in the ITT population with both baseline RHI lamina propria neutrophils and neutrophils in the epithelium subscores > 0 .
- Endpoints assessing histologic response will be evaluated in the subset of subjects in the ITT population with baseline RHI score ≥ 7 .
- Endpoints assessing subjects with a Geboes score ≤ 2 will be evaluated in the subset of subjects in the ITT population with a baseline Geboes score > 2 .
- The endpoint assessing steroid-free clinical remission at PCP Week 36 will be evaluated in the subset of subjects in the ITT population with an actual stratification value of yes for systemic corticosteroid use at baseline.
- Endpoints assessing the proportion of subjects with RHI score ≤ 3 will be evaluated in the subset of subjects in the ITT population with baseline RHI score > 3 .
- Endpoints assessing the proportion of subjects with fecal calprotectin, fecal lactoferrin, or CRP values below a certain threshold value will be evaluated in the subset of subjects in the ITT population who baseline value is above the threshold value for the endpoint.

For all applicable efficacy analyses, stratification factor values (systemic corticosteroid use at baseline [yes/no]) will be based on the values used for randomization, unless otherwise stated.

8.3. Analysis Methods

8.3.1. Primary Endpoint

8.3.1.1. Primary Analysis

The primary objective of the PCP will be evaluated by testing the superiority of each GB004 treatment group to the placebo treatment group with respect to the primary endpoint of the proportion of subjects with clinical remission at PCP Week 12 based on a Cochran-Mantel Haenszel (CMH) chi-squared test ([Mantel, 1959](#)) stratified by the randomization stratification factor of systemic corticosteroid use at baseline (yes/no) with a two-sided 0.050 level of significance for each comparison.

The Mantel-Fleiss criterion ([Mantel, 1980](#)) will be used to assess the validity of the chi-square approximation for the distribution of the CMH test statistic. In the case that the Mantel-Fleiss criterion is not at least 5, indicating lack of validity of the chi-square approximation due to stratum cell sizes that are too small, Pearson's chi-squared test will be used instead of the CMH chi-squared test in the primary analysis of the primary endpoint. In the rare case that expected cell frequencies are too small, Fisher's exact test will be used instead of Pearson's chi-squared test.

For the comparison of each GB004 treatment group versus placebo, the p-value from the CMH chi-squared test (or Pearson's chi-squared test and/or Fisher's exact test, as described above) will be reported. The number and proportion of subjects meeting the primary endpoint and corresponding 95% Wilson (Score) CIs ([Wilson, 1927](#)) will be summarized by treatment group.

The unstratified, absolute difference in proportion between each GB004 treatment group and placebo will be summarized, with the 95% CI for the unstratified, absolute difference based on the Newcombe continuity-corrected method ([Newcombe, 1998](#)). The estimated Mantel-Haenszel common odds ratio across strata and corresponding 95% CI will also be summarized.

The primary analysis of the primary endpoint will be based on application of ICE handling followed by NRI.

A bar graph of the proportion of subjects meeting the primary endpoint by treatment group will be presented.

Primary endpoint data will be presented in a by-subject data listing.

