2.6. Sample Size Determination

A total sample size of approximately 195 subjects (approximately 65 per treatment group, randomized 1:1:1, with stratification by systemic corticosteroid use at baseline [yes/no]) is estimated to provide approximately 80% power to detect a difference of 20.4% between each GB004 treatment group and placebo for the primary endpoint of proportion of subjects with clinical remission at PCP Week 12 based on a chi-squared test at an 0.050 two-sided level of significance. This assumes the proportion of subjects with clinical remission at PCP Week 12 is 10% in the placebo group and 30.4% in each GB004 treatment group and a dropout rate by PCP Week 12 of approximately 8%. Subjects with missing clinical remission status at PCP Week 12 will be considered as having not met the primary endpoint.

Using the same sample size assumptions as above for the primary endpoint of proportion of subjects with clinical remission at PCP Week 12 (ie, a difference of 20.4% between each GB004 treatment group and placebo, with a 10% proportion in the placebo group), there will be approximately 80% power for the secondary endpoint of the proportion of subjects with clinical remission at PCP Week 36 based on a chi-squared test at an 0.050 two-sided level of

significance. Subjects with missing clinical remission status at PCP Week 36 will be considered as having not met the endpoint.

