8.3.1.2.4. Sensitivity Analysis #4: Logistic Regression with ICE Handling and NRI Applied

In this sensitivity analysis, logistic regression modeling will be used to compare each GB004 treatment group with the placebo treatment group, after handling of ICEs and NRI are applied.

The logistic regression model will include covariates for treatment group, the randomization stratification factor of systemic corticosteroid use at baseline (yes/no), baseline Modified Mayo score, and region (Europe vs Rest of World).

The odds ratio (OR), corresponding asymptotic 95% CI, and p-value from the logistic regression model will be presented for the comparison of each GB004 treatment group versus placebo.

If the logistic regression model does not converge, covariates will be removed from the model, and the first reduced model that converges among reduced models with the below specified covariates will be utilized in the following order of priority:

- Treatment group, randomization stratification factor, and baseline Modified Mayo score
- Treatment group and randomization stratification factor
- Treatment group only

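### The primary analysis of Week 12 remission leaves baseline Modified Mayo score unused; if that score is prognostic, an adjusted risk difference would gain some precision at little cost

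*SAP*

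**What the plan says.** SAP 8.3.1.1 compares each GB004 arm with placebo by a CMH test "stratified by the randomization stratification factor of systemic corticosteroid use at baseline (yes/no) with a two-sided 0.050 level of significance for each comparison". If the Mantel-Fleiss criterion falls below 5, Pearson's test replaces CMH, and Fisher's exact test replaces Pearson's if expected cell counts are too small. Either replacement drops the steroid stratum. The effect measure is also unadjusted: "The unstratified, absolute difference in proportion between each GB004 treatment group and placebo will be summarized", with a continuity-corrected Newcombe interval. A Mantel-Haenszel odds ratio across the steroid strata is given as well. Protocol 9.4.1.1 names the same CMH approach.

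Baseline Modified Mayo score is a planned covariate in Sensitivity Analysis #4 (SAP 8.3.1.2.4), a logistic model with treatment, steroid stratum, "baseline Modified Mayo score, and region (Europe vs Rest of World"). That analysis reports a conditional odds ratio and its p-value. The score also defines subgroups (SAP Table 5) and optional interaction models (SAP 8.4).

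The sample size (SAP 2.6, protocol 9.2.1) is "based on a chi-squared test at an 0.050 two-sided level of significance", with no covariate.

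**The concern.** Remission is defined on the Modified Mayo scale, so the baseline value of that scale is the natural candidate for adjustment. All three of its components are entry criteria (protocol 5.1, criterion 3) and are reviewed before randomisation (protocol 1.3.1). Randomisation is stratified only by steroid use, so baseline score can differ between arms by chance. The SAP already adjusts its exploratory change-from-baseline endpoints for the baseline value in their main ANCOVA (SAP 8.3.4.1.2), but does not do so for the primary endpoint.

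At stake is some power in a trial sized at about 80% per comparison, and some width in the interval for the risk difference. The plan also takes its p-value and its interval from different methods: an uncorrected stratified test and a continuity-corrected unstratified interval.

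**Working it through.** **Inputs from the documents (SAP 2.6).** Rates "10% in the placebo group and 30.4% in each GB004 treatment group"; "approximately 65 per treatment group, randomized 1:1:1"; "a dropout rate by PCP Week 12 of approximately 8" percent; two-sided 0.05; missing status counted as no remission. The stated result is "approximately 80% power to detect a difference of 20.4% between each GB004 treatment group and placebo".

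**Reproducing the stated power.** For the uncorrected pooled chi-squared test,

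z = [Δ√n − 1.96·√(2p̄(1−p̄))] / √(p₀(1−p₀) + p₁(1−p₁)), and power = Φ(z).

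- Dropouts removed: n = 65 × 0.92 ≈ 60, Δ = 0.204, p̄ = 0.202. z = (1.580 − 1.113)/0.549 = 0.851, power **80.3%**.
- Dropouts counted as failures: n = 65, rates 0.10 × 0.92 = 0.092 and 0.304 × 0.92 = 0.280, Δ = 0.188, p̄ = 0.186. z = (1.513 − 1.078)/0.534 = 0.815, power **79.2%**.

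Both agree with about 80%. Simulated CMH power is also about 80% to 81%, with type I error of 4.7% to 5.1%. The planned test does what the plan claims.

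**Inputs that are assumptions.** The documents do not give the prognostic strength of baseline score, its distribution or the share of subjects on steroids. Assumed here: scores spread over 4 to 8 (the span of the SAP Table 5 bands), 35% on steroids, and an effect of score that is linear in the log-odds of remission.

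**Standardised risk difference.** Fit a logistic model with treatment, steroid stratum and baseline score. Predict each subject's remission probability under GB004 and under placebo, average each over all subjects, and take the difference. This targets the same marginal difference in proportions that SAP 8.3.1.1 reports. The simulation uses 65 per arm and 9.2% vs 28.0%, with an influence-function standard error, a degrees-of-freedom correction and a t reference:

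| Assumed log-odds slope per point | Adjusted power | CMH power |
|---|---|---|
| 0 | 80.5% | about 80% |
| −0.5 | 83.0% | about 80% |
| −0.8 | 84.5% | about 80% |

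**Why the correction is needed.** With 9.2% in both arms there are only about 2 × 65 × 0.092 ≈ 12 remissions per comparison. The uncorrected version then rejects 5.9% to 6.2% of the time, and the corrected version 5.1% to 5.5%.

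**Second calculation.** This one uses 60 per arm, 10% vs 30.4%, assumed shares of 12/23/30/25/10% for scores 4 to 8, 20,000 trials per scenario, and a score test for treatment in the logistic model. Variance is that of the standardised risk difference relative to the unadjusted one.

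| Assumed odds ratio per 1 SD lower score | CMH power | Adjusted score-test power | Variance change |
|---|---|---|---|
| 1.0 | 81.0% | 81.4% | +1.7% |
| 1.5 | 80.9% | 82.3% | −0.9% |
| 2.0 | 81.1% | 84.0% | −4.8% |
| 3.0 | 80.7% | 86.7% | −12.2% |

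With those shares the score has SD 1.17. A slope of −0.5 is therefore an odds ratio of exp(0.5 × 1.17) ≈ 1.8 per SD, and −0.8 is exp(0.8 × 1.17) ≈ 2.5. The two tables agree: a gain of about 3 points near the first value and 4 to 5 near the second (at odds ratio 2.5 the score test gives 85.7% against 81.1%).

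**Test against interval.** In simulation the Newcombe interval excluded zero in about 75% of trials, while CMH was significant in about 80%. CMH was significant with zero inside the interval in about 5.5% of trials, and this hardly changed with prognostic strength.

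**The case against.** The strongest reply is that nothing is broken. CMH stratified by the randomisation factor is valid, follows the protocol and has the planned power. A reader might infer from the unused covariate that the trial is underpowered, or that power is certainly being lost. The documents support neither: the stated power reproduces, and any loss depends on a prognostic strength that they do not give. For a weak to modest predictor (odds ratio 1.0 to 1.5 per SD) the gain is about 0 to 1 point. With a Wald test on the logistic coefficient, a non-prognostic score costs about 1 point.

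A second reply concerns the size of the gain. Without a small-sample correction, part of it comes from changing the test: at slope −0.5 an unadjusted Wald test had 81.0% power against 79.4% for CMH, and standardisation had 82.6%. Adjustment itself then added 1.6 points. At slope 0 standardisation lost to the unadjusted Wald test, 81.4% to 82.2%. This stands against any uncorrected version, which also rejects about 6% under the null in a plan with no multiplicity adjustment (SAP 8.1.3). With the correction, type I error is close to nominal and a gain remains.

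Third, the change is not merely wording. It departs from the test named in protocol 9.4.1.1, SAP Section 1 describes the SAP as finalised and approved, and Sponsor representatives on the DRC see unblinded emerging efficacy (protocol 9.5.1). That stands as a cost, and it is why the change must be recorded and made before Sponsor unblinding.

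A reader might also suggest promoting Sensitivity Analysis #4 unchanged. That would replace the marginal risk difference with a conditional odds ratio, and it carries region as a further covariate. Finally, the score is not strictly available for everyone: SAP 8.1.1.1 provides for missing baselines, and SAP 8.5.1 sets the diary subscores to missing with fewer than 3 usable days.

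**Conclusion.** The point holds as a conditional efficiency gain. The primary test is valid and meets its stated power. It and the risk difference leave out a baseline score that is available for essentially all subjects and that the SAP already models elsewhere. With a corrected adjusted analysis, power is about 80.5% if the score has no prognostic value, 83% at a slope of −0.5 and 84.5% at −0.8, against about 80% for CMH. The downside if the score is uninformative is close to nil: power is unchanged within simulation error and risk-difference variance rises by about 2%. These sizes rest on the assumed slopes, score spread and steroid share. That the planned p-value and interval can disagree does not depend on the slope.

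**What to change.** Before Sponsor unblinding:

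- Make the primary analysis a standardised (g-computation) risk difference from a logistic model with treatment, randomised steroid stratum and baseline Modified Mayo score only. Take the p-value and the 95% CI from it. At the planning rates there are only about 6 + 18 = 24 remissions per comparison, so add no further covariates.
- Name one variance estimator, with a degrees-of-freedom correction and a t reference.
- State whether the model is fitted pairwise or to all three arms.
- Give a rule for a missing baseline score, for example simple imputation blind to arm. This fills the covariate only; non-responder imputation of the outcome stays as planned.
- For non-convergence, follow the order in Sensitivity Analysis #4 (baseline score is removed before the stratum) and fall back to CMH.
- Keep CMH, with its Mantel-Fleiss, Pearson and Fisher steps, as a sensitivity analysis.
- For the secondary endpoints, use the matching baseline scores already listed in SAP 8.3.2.2.
- Record the departure from protocol 9.4.1.1 in SAP Section 10, which now declares no changes.

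Cost: no patients and no new data, but a documented change from the protocol's named test, somewhat more programming, and reliance on a small-sample correction with few events. It is a cheap improvement.
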